# Attachment I: Insufficiency of Protective Qi (IPQ) Index

Final score	Subscore C	Subscore B	Subscore A		
IPQ index, Weighted sum of Subscore Cs. Part I Wt.: 25%, Part II Wt.: 33.3%, Part III Wt.: 41.7%	Part I: Score of Cold History, Weighted sum of Subscore Bs. Ia1 Wt. 66.7%, Ia2 Wt. 33.3%	Part Ia1: Cold* frequency (in the past 2 month & recovery (total time if $\geq$ once), select from Subscore As one that applies	no Cold* at all	1	
			Once & recovered within 3day	2	
			Once & recovered within 1wk	3	
			Once & recovered within 2wk	4	
			Once & recovered $\geq$ 2 wk	5	
			Twice & recovered within 3day	6	
			Twice & recovered within 1wk	7	
			Twice & recovered within 2wk	8	
			Twice & recovered $\geq$ 2 wk	9	
			3 time or more	10	
		Part Ia2: Cold* related symptoms; Sum of Subscore As + 1	Sneezing	1 if yes	
			Coughing	1 if yes	
			Sweating	1 if yes	
			Nasal discharge or congestion	1 if yes	
			Itching or painful throat	1 if yes	
	Headache		1 if yes		
	Aversion to wind and cold		1 if yes		
	General pain and malaise		1 if yes		
	Part II, Score of Other IPQ symptoms, Weighted sum of Subscore Bs. Ib1 Wt. 50%, Ib2 Wt. 50%	Part IIa: Spontaneous sweating, Select from Subscore As one that applies	High fever ( $\geq$ 39.10C)	1 if yes	
			Don't readily sweat, or sweat only with intense physical activities	1	
			sweat with some slight physical activities like walking	2	
			Sweat spontaneously	3	
			Sweat heavily and instantly with physical activities	4	
		Part IIb: Aversion to wind or cold, Select from Subscore As one that applies	Sweat even without any physical activities	5	
			No aversion to wind or cold	1	
			Aversion to wind	2	
			Aversion to cold, but relieved by adding clothing	3	
			Aversion to both cold (but relieved by clothing) and wind, or susceptible to cold* when exposed to wind or cold weather	4	
			Aversion to cold (only relieved by clothing that cover whole body), very readily catch a cold* when exposed to wind or cold weather	5	
			Part III: Sign Score, Weighted sum of Subscore As. of Part I- IV; Part I Wt. 24%, Part II Wt. 40%, Part III, 20%, Part IV, 16%		Part I: weak or powerless pulse
Part II: chun-pulse superficial or weak					Scale 1-5
Part III: corpulent tongue or with white fur					Scale 1-5
Part IV: low voice					Scale 1-5

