## Attachment II: Insufficiency of Generic Qi (IGQ) Index

Final score	Subscore E	Subscore D	Subscore C	Subscore B	Subscore A	
IGQ index, Weighted sum of Subscore Es. Symptom Score Wt.: 40%, Sign Score Wt.: 60%	Symptom Score, select the highest one among Subscore Ds of Part I - VI	Part I: Protective Qi Insufficiency Score, Weighted sum of Subscore Cs. Part Ia Wt.: 47%, Part Ib Wt.: 53%	Part Ia: Score of Cold History, Weighted sum of Subscore Bs. Ia1 Wt. 66.7%, Ia2 Wt. 33.3%	Part Ia1: Cold* frequency (in the past 2 month & recovery (total time if $\geq$ once), select from Subscore As one that applies	no Cold* at all	1.00
					Once & recovered within 3day	1.44
					Once & recovered within 1wk	1.89
					Once & recovered within 2wk	2.33
					Once & recovered $\geq$ 2 wk	2.78
					Twice & recovered within 3day	3.22
					Twice & recovered within 1wk	3.67
					Twice & recovered within 2wk	4.11
					Twice & recovered $\geq$ 2 wk	4.56
					3 time or more	5.00
			Part Ia2: Cold* related symptoms; Sum of Subscore As + 0.5	Sneezing	0.5 if yes	
				Coughing	0.5 if yes	
				Sweating	0.5 if yes	
				Nasal discharge or congestion	0.5 if yes	
				Itching or painful throat	0.5 if yes	
				Headache	0.5 if yes	
				Aversion to wind and cold	0.5 if yes	
				General pain and malaise	0.5 if yes	
				High fever ( $\geq$ 39.10C)	0.5 if yes	
				Part Ib: Score of Other IPQ symptoms, Weighted sum of Subscore Bs. Ib1 Wt. 50%, Ib2 Wt. 50%	Part IIb1: Spontaneous sweating, Select from Subscore As one that applies	Don't readily sweat, or sweat only with intense physical activities
		sweat with some slight physical activities like walking	2			
		Sweat spontaneously	3			
		Sweat heavily and instantly with physical activities	4			
		Sweat even without any physical activities	5			
		Part IIb1: Aversion to wind or cold, Select from Subscore As one that applies	No aversion to wind or cold		1	
			Aversion to wind		2	
			Aversion to cold, but relieved by adding clothing		3	
			Aversion to both cold (but relieved by clothing) and wind, or susceptible to cold* when exposed to wind or cold weather		4	
			Aversion to cold (only relieved by clothing that cover whole body), very readily catch a cold* when exposed to wind or cold weather		5	
		Part II: Systemic Qi Insufficiency Score, average Subscore As of IIa-d	IIa: often feel limb weakness	Scale 1-5		
			IIb: often feel a lack of energy	Scale 1-5		
			IIc: often feel in low spirits	Scale 1-5		
			IID: often feel unwillingness to talk	Scale 1-5		

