#### **9.4.2 Analysis of the Efficacy Endpoint(s)**

Trial outcome measures, if they are continuous, will be evaluated by skewness and kurtosis for normality and expressed as mean (95% CI) if both measures were within the range of (2, -2); otherwise they will be expressed as median (95% CI) with specification. Given the potential effect of treatment time on trial outcomes, we will analyze the effect of  $\beta$ -glucan with adjustment by treatment time. This will be conducted by linear mixed regression [16] or Aligned Rank Transformation ANOVA [17] if assumptions of the regression model were not satisfied. Categorical outcomes will be derived from conventional PQD diagnosis. The effect of  $\beta$ -glucan will be analyzed using generalized mixed linear model [18] for conventional PQD diagnosis.

For all statistical analyses, differences with a  $P < 0.05$  (two tailed) will be considered significant.

Other details analysis of the primary endpoints are described as follows:

- The PQi status of each participant at baseline and each follow-up visit will be measured by on-site investigators (licensed TCM practitioners) through a standardized quantitative assessment (Table 1 & Table 2). Each health condition relevant to PQD (i.e. cold frequency, symptoms, and signs) will be scored on a designed scale (ranging 1-10, with higher number indicating more severe deficiency) based on a set of standardized and specified criteria (Table 2). The sub-scores are then weighted (cold history 25%, symptoms 33.3%, signs: 41.7%) to arrive at a final PQD severity score. This score is on a 1-5 scale, with 5 being the most severe deficiency. The change of the score from baseline, indicating the treatment effect, will be calculated and analyzed by statistical means.
- PQi status of each participant at baseline and each follow-up visit will be measured by on site-investigators (licensed TCM practitioners) through non-standardized, qualitative traditional assessment. The status was characterized by non-PQD or PQD. The change of PQi status from baseline, indicating the treatment effect, will be calculated and analyzed by categorical statistic.

Other details analysis of the secondary endpoints are described as follows:

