**Table 2: Standardized criteria for PQi severity score assessment**

Candidate Parameter		Method of measurement and scores	
Cold Frequency	TCM Inquiry (Cold frequency)	No cold in the past 2 months	0
		Once in the past 2 months	1
		Twice in the past 2 months	2
		3 times or more in the past 2 months	3
Symptoms of PQD	TCM Inquiry (Spontaneous sweating)	No spontaneous sweating, sweat only with intense physical activities	0
		Sweat with routine physical activities	1
		Sweat heavily with routine physical activities	2
		Sweat with slight physical activities like walking	3
		Sweat spontaneously	4
	TCM Inquiry (Aversion to wind & cold)	No aversion to wind or cold	0
		Aversion to wind	1
		Aversion to cold, but relieved by adding light clothing	2
		Aversion to both cold (but relieved by light clothing) and wind, or susceptible to cold when exposed to wind or cold	3
		Aversion to cold (only relieved by thick clothing that covers whole body); or very easily catch a cold when exposed to wind or cold	4
Sign of PQD	TCM Auscultation (Low voice & apathy)	The participant's voice is loud & clear at a distance of 2m from the investigator	0
		The participant can be heard & understood at 2m from the investigator, but the voice is recognizably weak.	1
		The participant's voice is clearly low at 2m from the investigator & needs much attention to understand.	2
		The participant can be heard from 2m but need repeated clarification.	3
		The participant cannot be heard with a clear understanding at a distance of 2m.	4
	TCM Inspection (Tongue)	The tongue looks light red with thin white coating and is of proper size.	0
		The tongue looks pale in color with white coating; however, the tongue is of proper size & has no tooth mark on the sides.	1
		The tongue looks pale with white coating. This size is slightly larger than normal. Tooth-marks are visible but are limited to part(s) of the tip and sides of the tongue.	2
		The tongue looks pale with white coating. This size is significantly larger than normal. Tooth-marks are visible along the full length of the tip and sides of the tongue.	3
	TCM Palpation (Overall Pulse  )	Normal pulse	0
		Deficient Pulse is detectable but not apparent	1
		Apparent Deficient Pulse	2
	TCM Palpation (Cun Puls  )	Normal pulse	0
		The pulse shows characteristics of Floating or Deficient Pulse, but not both.	1
		Floating pulse is present, Deficient Pulse is detectable but not apparent.	2

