### Subject Record at Follow-up

#### Participant questionnaire – PQi and GQi Evaluation Questionnaire

##### Part I

Do you have a history of **catching** a cold\* (\*, defined by TCM) in the past year? If no, please proceed to Part II of this section; if yes, please fill out the following blanks.

1. How many times did you **catch** a cold\* in the **past year**?

i. Once

duration:

ii. Twice

duration of cold #1:

duration of cold #2:

iii. 3 times or more

duration of cold #1:

duration of cold #2:

duration of cold #3:

duration of other colds:

iv. During the above colds\*, did you experience any of the following symptoms:

- Sneezing
- Coughing
- Sweating
- Nasal discharge or congestion
- High fever (body temperature  $> 39.1^{\circ}\text{C}$ )
- Itching or painful throat
- Headache
- Aversion to wind and cold
- General pain and malaise

2. How many times did you **catch** a cold\* **last winter (2017 – 2018)**?

i. Once

duration:

ii. Twice

duration of cold #1:

duration of cold #2:

iii. 3 times or more

duration of cold #1:

duration of cold #2:

duration of cold #3:

duration of other colds:

iv. During the above colds\*, did you experience any of the following symptoms:

- Sneezing
- Coughing
- Sweating
- Nasal discharge or congestion
- High fever (body temperature > 39.1C)
- Itching or painful throat
- Headache
- Aversion to wind and cold
- General pain and malaise

3. How many times did you **catch** a cold\* in the **last two months**?

i. Once

duration:

ii. Twice

duration of cold #1:

duration of cold #2:

iii. 3 times or more

duration of cold #1:

duration of cold #2:

duration of cold #3:

duration of other colds:

iv. During the above colds\*, did you experience any of the following symptoms:

- Sneezing
- Coughing
- Sweating
- Nasal discharge or congestion
- Itching or painful throat
- Headache
- Aversion to wind and cold
- General pain and malaise
- High fever (body temperature > 39.1C)

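### V4.0 scores the primary PQD index from Tables 1-2, but its follow-up form and 1-10 item wording partly follow an unwithdrawn Attachment I, and neither rule gives the stated 1-5 range

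*Protocol*

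**What the plan says.** **The cited rule.** In the combined protocol and SAP (V4.0), inclusion criterion 6, the screening text in section 5.5, section 8.1 and section 9.4.2 all point to Tables 1 and 2. Section 9.4.2 gives the weighting: "The sub-scores are then weighted (cold history 25%, symptoms 33.3%, signs: 41.7%) to arrive at a final PQD severity score". In Table 2 the cold component is a count over two months, from 0 up to 3 for "3 times or more in the past 2 months". It scores neither duration nor cold symptoms. Section 9.4.2 and the note under Table 1 both give the final score a 1-5 range.

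**The other rule.** Attachment I in the Protocol file states "IPQ index, Weighted sum of Subscore Cs. Part I Wt.: 25%, Part II Wt.: 33.3%, Part III Wt.: 41.7" (per cent). Its cold component is itself a composite: "Part I: Score of Cold History, Weighted sum of Subscore Bs. Ia1 Wt. 66.7%, Ia2 Wt. 33.3" (per cent). The first part grades the number of colds by recovery time on ten steps, with "Once & recovered within 3day" scoring 2. The second is "Part Ia2: Cold* related symptoms; Sum of Subscore As + 1", where nine symptoms count 1 each. The attachment carries no date, V4.0 does not cite it, and nothing marks it as withdrawn.

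**What V4.0 collects.** Appendix 4, Part I asks for the length of each cold ("duration of cold #1" and so on) and for the same nine symptoms. Part II offers the attachment's five sweating options, and Part IX scores the four signs on 1-5. Section 9.4.2 says items are scored on 1-10, a scale that no Table 2 item has.

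**The concern.** The primary endpoint, and entry to the trial, depend on one number. V4.0 names one rule for that number, describes item scales that do not belong to the rule, and collects its follow-up data on a form built largely for the other rule. An analyst working from the file would have to decide how a 1-5 sign score becomes a 0-2, 0-3 or 0-4 level, what to do with the recorded durations and symptoms, and on which scale 1.8 is to be read. A benefit through shorter or milder colds counts on one rule and is invisible on the other.

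**Working it through.** **1. Is it the same instrument?** Attachment I's sign weights times 41.7% are 0.24 × 41.7 = 10.0 (overall pulse), 0.40 × 41.7 = 16.7 (cun pulse), 0.20 × 41.7 = 8.3 (tongue) and 0.16 × 41.7 = 6.7 (voice). These are Table 1's sign weights. The weighting is shared and the item scoring differs.

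**2. Items side by side.**

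| Item | Table 2 | Attachment I | Appendix 4 form |
|---|---|---|---|
| Colds | count, 0-3 | frequency with recovery 1-10; symptoms 1-10 | count, durations, nine symptoms |
| Sweating | 0-4, two levels for routine activity | 1-5, no routine-activity level | Attachment I's options |
| Signs | pulse 0-2, cun 0-3, tongue 0-3, voice 0-4 | 1-5 | 1-5 |

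**3. The stated 1-5 range.**

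Attachment I = 0.25 × (0.667 × frequency + 0.333 × symptoms) + 0.333 × (mean of sweating and aversion) + 0.417 × (weighted signs). All signs are taken as 1-5, as Attachment II has them.
- Lowest: 0.25 + 0.333 + 0.417 = 1.00.
- Highest: 0.25 × 10 + 0.333 × 5 + 0.417 × 5 = 6.25.

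Tables 1-2 = 0.25 × cold + 0.167 × sweating + 0.167 × aversion + 0.083 × tongue + 0.067 × voice + 0.10 × pulse + 0.167 × cun.
- Lowest: 0.
- Highest: 0.750 + 0.668 + 0.668 + 0.249 + 0.268 + 0.200 + 0.501 = 3.304.

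Neither gives 1-5. Adding 1 to every Table 2 level gives 1.00-4.31, still short of 5.

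**4. Share of the attainable range.**

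| Part | Stated | Attachment I (span 5.25) | Tables 1-2 (span 3.304) |
|---|---|---|---|
| Cold history | 25% | 0.25 × 9 = 2.25, 42.9% | 0.75, 22.7% |
| Symptoms | 33.3% | 0.333 × 4 = 1.332, 25.4% | 1.336, 40.4% |
| Signs | 41.7% | 0.417 × 4 = 1.668, 31.8% | 1.218, 36.9% |

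**5. Can the two rules disagree?** All other items are held fixed in each case.
- *One cold at each visit.* At first it lasts 2 weeks or more with six symptoms (frequency 5, symptoms 7); later it clears within 3 days with two symptoms (2 and 3). Attachment I falls by 0.25 × 0.667 × 3 + 0.25 × 0.333 × 4 = 0.50 + 0.33 = 0.83. Tables 1-2 do not move.
- *Opposite directions.* One cold of 2 weeks or more with nine symptoms, then two colds cleared within 3 days with one symptom. Attachment I: 0.25 × (0.667 × (6 − 5) + 0.333 × (2 − 10)) = −0.50. Tables 1-2: 0.25 × (2 − 1) = +0.25.
- *Sweating.* A move from sweating on walking to heavy sweating with activity, treating the two documents' heavy-sweating options as equivalent. Attachment I: 0.333 × 0.5 × (4 − 2) = +0.33. Tables 1-2: 0.167 × (2 − 3) = −0.17.

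**6. The >1.8 threshold.** One cold of 2 weeks or more with four symptoms, everything else at its lowest level, scores 0.25 × (0.667 × 5 + 0.333 × 5) + 0.333 + 0.417 = 2.00 on Attachment I and 0.25 on Tables 1-2. The value 1.8 lies at (1.8 − 1)/5.25 = 15% of the attainable span on Attachment I, 1.8/3.304 = 54% on Tables 1-2, and (1.8 − 1)/4 = 20% of a true 1-5 scale.

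**7. Would rescaling alone settle it?** Attachment II maps the frequency item linearly to 1-5 and the symptom item to 0.5-5 ("Part Ia2: Cold* related symptoms; Sum of Subscore As + 0.5"). With that scaling Attachment I would run 0.96-5.00, with cold history 0.25 × (0.667 × 4 + 0.333 × 4.5) = 1.04 of 4.04, or 25.8%. The first example in step 5 would still give 0.25 × (0.667 × 3 × 4/9 + 0.333 × 4 × 0.5) = 0.39 against 0. Rescaling roughly restores the weights but does not remove the disagreement.

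**The case against.** The best defence is that V4.0 has already chosen: every eligibility and endpoint reference is to Tables 1-2, and Attachment I uses older-looking terms and is never cited. That stands. A reader might infer two co-equal primary endpoints with no governing rule; the documents do not support it. What the defence leaves unexplained is the Appendix 4 form, the 1-10 wording and the failure of Tables 1-2 to yield 1-5. The 1-10 wording might instead echo the screening form in Appendix 1, which also rates on 1-10, but that is not Table 2 either.

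Three other strong readings go too far.
- The 42.9% might be read as cold history dominating the score in practice. It is a share of attainable range. Influence on a composite depends on observed item variances, and the documents give none. On the cited rule the share is 22.7%, close to the stated 25%.
- The 0.83 might be set against a pilot mean change worked back from the sums of squares in section 9.2. Their labels do not settle what was summed, and the pretest scores were adjusted for regression to the mean, so they supply no usable yardstick.
- V4.0 is dated February 2022 and enrolment was planned for December 2018 to March 2019, so a reader might suspect that the scoring was chosen after the data. Nothing in the documents shows this.

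**Conclusion.** The point holds in a limited form. Tables 1-2 are the cited rule, but V4.0 cannot be applied as written: its item-scale wording does not fit Table 2, its follow-up form does not record Table 2's sweating and sign levels, and the stated 1-5 range follows from neither rule. The primary score and the threshold therefore cannot be computed consistently from the text. The ranges and shares follow directly from the printed weights and levels, given 1-5 for every sign in Attachment I. The worked participants show that the rules can disagree, even in direction. How often this happens, and whether it would alter the trial result, cannot be said without item-level data.

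**What to change.** - Confirm in section 9.4.2 that one rule (as now cited, Tables 1-2) governs both the primary endpoint and the >1.8 threshold, and mark Attachment I as superseded, or the reverse.
- Correct the 1-10 wording. Put the items of the governing rule on a common scale so that the 1-5 range and the 25/33.3/41.7 weights hold, or restate the range.
- State how Appendix 4 answers for sweating and signs convert to Table 2 levels. Reconcile the scale on which 1.8 was derived with the scale on which it is applied.
- Report the index with the alternative cold-item scoring as a sensitivity analysis.

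The cost is wording and one extra analysis. The follow-up form holds the cold data for both versions, so the sensitivity analysis covers the cold item and extends to the whole index only once a conversion is stated. One check is needed first. The Appendix 1 screening form asks about three months and omits the nine symptoms, and section 5.5 describes re-assessment with Appendix 4 only for participants who return after screening. For those enrolled on the screening day, confirm that an Appendix 4 baseline exists.

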## Attachment II: Insufficiency of Generic Qi (IGQ) Index

Final score	Subscore E	Subscore D	Subscore C	Subscore B	Subscore A	
IGQ index, Weighted sum of Subscore Es. Symptom Score Wt.: 40%, Sign Score Wt.: 60%	Symptom Score, select the highest one among Subscore Ds of Part I - VI	Part I: Protective Qi Insufficiency Score, Weighted sum of Subscore Cs. Part Ia Wt.: 47%, Part Ib Wt.: 53%	Part Ia: Score of Cold History, Weighted sum of Subscore Bs. Ia1 Wt. 66.7%, Ia2 Wt. 33.3%	Part Ia1: Cold* frequency (in the past 2 month & recovery (total time if $\geq$ once), select from Subscore As one that applies	no Cold* at all	1.00
					Once & recovered within 3day	1.44
					Once & recovered within 1wk	1.89
					Once & recovered within 2wk	2.33
					Once & recovered $\geq$ 2 wk	2.78
					Twice & recovered within 3day	3.22
					Twice & recovered within 1wk	3.67
					Twice & recovered within 2wk	4.11
					Twice & recovered $\geq$ 2 wk	4.56
					3 time or more	5.00
			Part Ia2: Cold* related symptoms; Sum of Subscore As + 0.5	Sneezing	0.5 if yes	
				Coughing	0.5 if yes	
				Sweating	0.5 if yes	
				Nasal discharge or congestion	0.5 if yes	
				Itching or painful throat	0.5 if yes	
				Headache	0.5 if yes	
				Aversion to wind and cold	0.5 if yes	
				General pain and malaise	0.5 if yes	
				High fever ( $\geq$ 39.10C)	0.5 if yes	
				Part Ib: Score of Other IPQ symptoms, Weighted sum of Subscore Bs. Ib1 Wt. 50%, Ib2 Wt. 50%	Part IIb1: Spontaneous sweating, Select from Subscore As one that applies	Don't readily sweat, or sweat only with intense physical activities
		sweat with some slight physical activities like walking	2			
		Sweat spontaneously	3			
		Sweat heavily and instantly with physical activities	4			
		Sweat even without any physical activities	5			
		Part IIb1: Aversion to wind or cold, Select from Subscore As one that applies	No aversion to wind or cold		1	
			Aversion to wind		2	
			Aversion to cold, but relieved by adding clothing		3	
			Aversion to both cold (but relieved by clothing) and wind, or susceptible to cold* when exposed to wind or cold weather		4	
			Aversion to cold (only relieved by clothing that cover whole body), very readily catch a cold* when exposed to wind or cold weather		5	
		Part II: Systemic Qi Insufficiency Score, average Subscore As of IIa-d	IIa: often feel limb weakness	Scale 1-5		
			IIb: often feel a lack of energy	Scale 1-5		
			IIc: often feel in low spirits	Scale 1-5		
			IID: often feel unwillingness to talk	Scale 1-5		
		Part III: Lung* Qi Insufficiency Score, average Subscore As of IIIa-d	IIIa: often feel shortness of breath	Scale 1-5		
			IIIb: often have a cough	Scale 1-5		
			IIIc: often have thin sputum	Scale 1-5		
			IIId: often feel timidity	Scale 1-5		
		Part IV: Spleen* Qi Insufficiency Score, average Subscore As of IVa-c	IVa: often have poor appetite	Scale 1-5		
			IVb: have loose stools	Scale 1-5		
			IVc: often have abdominal discomfort feeling after eating	Scale 1-5		
Part V: Heart* Qi Insufficiency Score, average Subscore As of Va-c	Va: often feel palpitations	Scale 1-5				
	Vb: often feel depressed	Scale 1-5				
	Va: frequent urination	Scale 1-5				
Part VI: Kidney* Qi Insufficiency Score, average Subscore As of VIa-c	VIb: often feel soreness of lower back	Scale 1-5				
	VIc: have cold limbs especially legs	Scale 1-5				
	Part I: weak or powerless pulse	Scale 1-5				
	Part II: chun-pulse superficial or weak	Scale 1-5				
Sign Score, Weighted sum of Subscore As. Part I- IV; Part I Wt. 24%, Part II Wt. 40%, Part III, 20%, Part IV, 16%	Part III: corpulent tongue or with white fur	Scale 1-5				
	Part IV: low voice	Scale 1-5
